10.7 ANALYSIS OF EXPLORATORY ENDPOINTS

- The uptake of ^{18}F -DCFPyL PET/CT will be correlated with CT/MRI grade by Kendall's tau-b correlation.

- The uptake of ¹⁸F-DCFPyL PET/CT will be correlated with tumor tissue histological PSMA expression by Kendall's tau-b correlation.
- The uptake of ¹⁸F-DCFPyL PET/CT measured by maximum Standard Uptake Value (SUV) will be correlated with ¹⁸F-FDG uptake by Spearman rank correlation. These SUV uptake measurements will also be correlated with PSMA expression as determined by standard histological assessment of tumor tissue.
- Uptake of ¹⁸F-DCFPyL PET/CT will be correlated with 5 year progression free survival (via scans collected from local providers during routine follow up) and 5 year overall survival by Cox regression analysis.
- Descriptive statistics will be used to summarize tumor biomarkers in blood and tissue samples.

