10.4 SAMPLE SIZE DETERMINATION

Sample size was calculated such that the limits of the 95% expected confidence interval to the true lesion level positive predicted value is less than 15%. The lesion level positive predictive value is the proportion of biopsy positive lesions. Assume 80% of the participants enrolled to the study each have 1-2 lesions identified by ^{18}F -DCFPyL PET/CT with 0.2 modest inter-lesion correlation, and the positive predictive value is 70%. A sample size of 40 evaluable participants accrued to the study produces a two-sided 95% confidence interval with the distance from the positive predictive value to the limits equal to 0.148. An evaluable participant is defined as a participant who completes all required study procedures. To account for inevaluable participants, the accrual ceiling will be set to 50.

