10.5 ANALYSIS OF THE PRIMARY ENDPOINT

The point estimates and 95% confidence intervals of the positive predictive value of ^{18}F -DCFPyL PET/CT will be reported in which the confidence limits are the 2.5th and 97.5th percentile of the 2000 bootstrap samples obtained by random sample without replacement at the participant level to account for inter-lesion correlation.

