10.6 ANALYSIS OF THE SECONDARY ENDPOINTS

- The lesion level sensitivity, specificity and positive predictive value of ^{18}F -DCFPyL PET/CT and CT/MRI will be calculated and compared. The confidence interval for each estimate will be obtained from the bootstrap samples as described in **10.5** and the difference in the estimates between the imaging modalities will be compared by the Wald test with the standard error calculated from the bootstrap samples.
- For ^{18}F -DCFPyL PET/CT positive participants who undergo local treatment for HCC, change in ^{18}F -DCFPyL PET/CT uptake between pre- and post-treatment of tumor or tumor bed will be compared by paired Wilcoxon test.

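### The uptake analyses in 10.6 and 10.7 name no unit of analysis and make no allowance for several lesions per participant; pooling lesions would push the Wilcoxon test modestly above its nominal level

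*Combined protocol and SAP*

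**What the plan says.** All references are to the Combined protocol and SAP.

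- **Clustering is recognized for accuracy.** Section 10.4 begins "Assume 80% of the participants enrolled to the study each have 1-2 lesions identified by" the PET/CT, "with 0.2 modest inter-lesion correlation, and the positive predictive value is 70" percent. Section 10.5 resamples "at the participant level to account for inter-lesion correlation". The first bullet of 10.6 reuses that bootstrap for sensitivity, specificity and PPV.
- **It is not mentioned for uptake.** The second bullet of 10.6 serves a secondary endpoint. It takes change in uptake in the tumor or its bed, among PET-positive participants who receive local treatment, and says this "will be compared by paired Wilcoxon test". In 10.7, uptake "will be correlated with tumor tissue histological PSMA expression" and with CT/MRI grade by Kendall's tau-b, and with FDG uptake by Spearman's coefficient. These analyses are exploratory.
- **The measurements are made per lesion.** Section 6.3.1.1 extracts SUVmax from a volume of interest for each target lesion. Section 5.2.1 assigns a single core from each lesion to immunohistochemistry and PSMA staining. Section 3.1 allows more than one lesion to be biopsied in a procedure.

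Neither the Wilcoxon bullet nor 10.7 gives a rule for reducing several lesions to one value.

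**The concern.** The three rank methods, in their ordinary form, assume independent observations. Two lesions in one participant share a liver and a scan, and often a treatment, so their uptake values are likely to be positively related. An analyst following the text could enter each lesion as a separate row, which would make p-values too small. An analyst could also choose one lesion per participant after seeing the data. The plan rules out neither.

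The Wilcoxon test matters most. It is the only test that section 10 names for the secondary objective on treatment response, and its sensitivity to clustering is greater than that of the correlations.

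**Working it through.** **Inputs.** From 10.4: 40 evaluable participants, 80% with PET-identified lesions (32), one or two lesions each, correlation 0.2, PPV 0.70. The share *f* of the 32 with two lesions is not stated and must be assumed. The 0.2 is given for PPV, so using it for uptake is also an assumption; 0.5 and 0.8 are added to show a range.

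**Step 1: reproduce the plan's figure to find a plausible *f*.** Lesions L = 32(1 + f). Design effect DE = 1 + 0.2 × 2f/(1 + f). Half-width = 1.96 × √(0.70 × 0.30 × DE / L).

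At f = 0.25, L = 40 and DE = 1 + 0.2 × 0.4 = 1.08, so the half-width is 1.96 × √(0.21 × 1.08 / 40) = 0.1476. This agrees with the plan's interval "with the distance from the positive predictive value to the limits equal to 0.148". One lesion each gives 0.159, half with two gives 0.138, and all with two gives 0.123. About a quarter with two lesions therefore fits the plan's own calculation.

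**Step 2: true error if lesions are pooled.** A nominal two-sided 5% test that ignores clustering has actual error 2 × [1 − Φ(1.96/√V)].

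- Signed-rank test of change: V = 1 + ρ × 2f/(1 + f).
- Rank correlation: V = 1 + ρX × ρY × 2f/(1 + f), because clustering matters only through the product of the two within-participant correlations. At 0.2 in both, that product is 0.04.

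Example: f = 0.25 and ρ = 0.2 give V = 1.08 for the signed-rank test, hence 5.9%; for a rank correlation V = 1 + 0.04 × 0.4 = 1.016, hence 5.2%.

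The table gives the formula result for each test, with simulated rates in parentheses (32 participants; 6,000 runs at f = 0.25, 5,000 at the others). For the correlations the simulated pair is Spearman, Kendall.

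| Correlation | Test | f = 0.25 | f = 0.50 | f = 1 |
|---|---|---|---|---|
| 0.2 | Wilcoxon | 5.9% (5.8) | 6.6% (6.4) | 7.4% (7.1) |
| 0.2 | Rank correlation | 5.2% (5.1, 4.7) | 5.3% (5.4, 5.3) | 5.5% (5.7, 5.7) |
| 0.5, assumed | Wilcoxon | 7.4% (7.3) | 9.0% (8.2) | 11.0% (10.0) |
| 0.5, assumed | Rank correlation | 6.2% (6.4, 6.3) | 7.0% (6.8, 6.5) | 8.0% (8.4, 7.8) |
| 0.8, assumed | Wilcoxon | 8.8% (9.4) | 11.4% (11.6) | 14.4% (14.4) |
| 0.8, assumed | Rank correlation | 8.0% (8.1, 7.6) | 10.1% (9.3, 8.4) | 12.6% (12.0, 11.5) |

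The Monte Carlo standard error near 5% is √(0.05 × 0.95 / 5,000) = 0.3 points. With no correlation and f = 0.25, the simulated Wilcoxon rate was 5.6%, so the 5.9% in the first row rests on the formula more than on the simulation.

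**Step 3: one value per participant.** Taking each participant's mean over lesions gave simulated error of 4.3 to 5.7% for Wilcoxon and Spearman in every setting.

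**Step 4: can the 10.5 bootstrap be reused?** Not as written. It draws participants without replacement. If all are drawn, every sample is the original one: a check with 32 binary values gave a bootstrap standard error of 0, against 0.081 with replacement.

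**The case against.** The strongest reply is that the lesion as unit is an inference. Where the plan means lesions it says so, in the accuracy endpoint of 10.2, in 10.4 and in the first bullet of 10.6. The Wilcoxon bullet is framed by participants, and the reference to tumor or tumor bed says where uptake is measured, not how many values each participant contributes. With one value each there is no inflation. This stands: what the documents establish is that the unit is unspecified, not that lesions will be pooled.

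Second, 10.7 states no alpha, p-value or interval for the correlations, and 10.6 states no interval for the Wilcoxon analysis. No decision rule or sample size depends on any of them. This also stands, and it limits the importance of the point.

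Third, the post-treatment scan requires a positive baseline scan and biopsy-confirmed HCC, so the Wilcoxon population is smaller than 32. With f = 0.25, a second lesion's chance of also being negative gives 0.30² + 0.2 × 0.21 = 0.132 for both negative, so about 24 × 0.70 + 8 × (1 − 0.132) = 23.7 participants. This is correct but changes little, because V depends on the share with two lesions and not on the number of participants.

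A reader might infer something stronger: that the plan applies lesion-level tests throughout, so that all these p-values are materially wrong, with error of 12 to 15%. The documents do not support that. For Kendall and Spearman at the plan's correlation, the error cannot be told from 5%. For the Wilcoxon test, error near 14% needs an assumed correlation of 0.8 and two lesions in every participant, and that lesion split implies a half-width of 0.123, not the stated 0.148.

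**Conclusion.** The point holds as a minor but real gap. The plan allows for correlated lesions in its accuracy analyses, then names ordinary rank methods for measurements made per lesion, without a unit of analysis or a rule for multiple lesions.

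If lesions are pooled as independent, the Wilcoxon test has true error of about 6% at the plan's correlation and the lesion split that fits its precision figure, and about 7% if everyone has two lesions. The ranges at assumed correlations of 0.5 and 0.8 are about 7 to 11% and 9 to 14%. The correlations are affected less: negligibly at 0.2, about 6 to 8% at 0.5 in both variables, and about 8 to 13% at 0.8 in both.

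These sizes depend on pooling, on the assumed share with two lesions, and on correlations for uptake that the documents do not give. Nor should 10.5 be read as a working correction that merely needs extending, since its resampling wording is itself defective.

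**What to change.** - **State the unit of analysis** for each uptake analysis in 10.6 and 10.7. Include the Cox regression in 10.7: survival is one outcome per participant, so lesion-level rows would count it twice.
- **Wilcoxon (10.6):** use one prespecified value per participant, for example the mean over treated target lesions, or a clustered signed-rank test.
- **Kendall and Spearman (10.7):** take intervals from a bootstrap that resamples participants, keeping all lesions of a drawn participant together.
- **Section 10.5:** change the resampling to with replacement before the method is reused.

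The cost is a few sentences, and most of the code is already needed for 10.5. Intervals will be slightly wider, and one value per participant gives up some lesion-level information.

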1.1.3 Exploratory Objectives

- Compare the distribution of ¹⁸F-DCFPyL uptake with standard of care CT and/or MRI.
- Compare focal abnormal ¹⁸F-DCFPyL uptake with focal abnormalities identified on ¹⁸F-FDG PET/CT.
- Compare PSMA expression with ¹⁸F-DCFPyL uptake.
- Compare tumor viability and metabolism determined by ¹⁸F-FDG PET imaging with ¹⁸F-DCFPyL uptake.
- Evaluate ¹⁸F-DCFPyL uptake with 5 year overall survival and 5 year progression free survival.
- Evaluate tumor biomarkers in blood, urine and tissue samples.

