Tumor uptake was much higher with ¹⁸F-DCFPyL than ¹⁸F-DCFBC and increased with time. Focal radiotracer activity could be seen in some lesions at the earliest imaging point at 5 minutes and all known lesions were visualized with highest uptake after 2 hours post-injection. ¹⁸F-DCFPyL uptake identified cancer lesions in the bone, prostate, lymph nodes and soft tissue. They did note that most lesions were visualized by 1 hour post-injection; however, there were a few small lesions only visible at 2 hours. They suggested that participants with biochemical recurrence might be best imaged at the 2 hour point (**Figure 1**).

[figure not shown]

Figure 1. *18F-DCFPyL PET images of a prostate cancer participant with multiple bone and lymph node disease.*

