6.3.1.1 Image Analysis

Target Lesions: Images will be analyzed by MIB staff by identifying, recording and measuring measurable target lesions. A segmentation tool will be applied to generate semi-automated volume of interests (VOI) within the target lesion(s). Maximum standardized uptake value (SUV_{max}) and tumor volumes will be extracted from the generated target lesion(s) VOIs. ^{18}F -DCFPyL uptake in major organs and bone marrow will also be measured and mean SUV values will be extracted.

All other lesions (or sites of disease) including any measurable lesions should be identified as non-target lesions and should also be recorded.

Antitumor effect: To determine whether uptake of ^{18}F -DCFPyL correlates with response to therapy, target tumor(s) imaging PET parameters, including SUV_{max} , and tumor volume will be compared between responders vs non-responders. Participant response will be based on RECIST 1.1. criteria and clinical assessment.

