10.3 EXPLORATORY ENDPOINTS

- Correlate the intensity of uptake of ^{18}F -DCFPyL PET/CT with respect to the CT and/or MRI tumor grade.
- Correlate tumor tissue histological PSMA expression with the intensity of uptake of ^{18}F -DCFPyL PET/CT.
- Compare tumor viability and metabolism determined by ^{18}F -FDG PET imaging with ^{18}F -DCFPyL uptake.
- ^{18}F -DCFPyL intensity of uptake (expressed as the maximum standard uptake value – SUVmax) and tumor volume will be correlated with 5 year overall survival, and 5 year progression free survival.
- Evaluate tumor biomarkers in blood, urine and tissue samples.

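### Tumor volume is named with SUVmax as a survival endpoint in 10.3 but has no analysis in 10.7, and a hazard ratio for uptake could partly reflect tumor size

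*Combined protocol and SAP*

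**What the plan says.** All references are to the combined protocol and SAP.

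- **1.1.3 Exploratory Objectives** names uptake only: to evaluate "uptake with 5 year overall survival and 5 year progression free survival".
- **10.3 Exploratory Endpoints** names two quantities. The first is "intensity of uptake (expressed as the maximum standard uptake value", that is, SUVmax. The second is tumor volume: "tumor volume will be correlated with 5 year overall survival, and 5 year progression free survival".
- **10.7 Analysis of Exploratory Endpoints** gives the method. Uptake on "PET/CT will be correlated with 5 year progression free survival", and on "5 year overall survival by Cox regression analysis". No second predictor and no covariate is listed, and volume appears nowhere in 10.7.
- **6.3.1.1 Image Analysis** shows that the data will exist: SUVmax "and tumor volumes will be extracted from the generated target lesion(s) VOIs". Other lesions are to be identified and recorded as non-target, with no volume extraction stated for them. The same section compares SUVmax and volume between responders and non-responders, but that concerns treatment response, not survival.

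**The concern.** There are two consequences of different kinds.

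The first is a gap in the text. One of the two predictors promised in 10.3 has no planned analysis, so whether and how volume is modelled would be settled after the data are seen.

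The second is interpretive. If SUVmax tends to be higher in larger tumors, and participants with larger tumors progress or die sooner, a Cox model containing only uptake credits uptake with part of the size effect. Section 1.3.3 cites a small series in advanced HCC in which SUVmax on a PSMA tracer correlated with overall survival, so a similar result here may well be read as prognostic. The reader would want to know whether it adds anything to tumor size.

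**Working it through.** **The plan's own figures.** The plan gives no event count, effect size or precision for the Cox analysis. Its one computed precision figure is the 0.148 distance to the confidence limits in 10.4. That figure is reproducible if 32 participants (80% of 40) contribute 40 lesions, 24 participants with one and 8 with two. This lesion mix is my assumption. The design effect is 1 + (56/40 − 1) × 0.2 = 1.08, and 1.96 × √(0.7 × 0.3 × 1.08/40) = 0.1476. It concerns the positive predictive value and has no bearing on this point.

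**Inputs for the check.** From the documents: 40 evaluable participants (10.4) and 5 years of follow-up (3.1, 3.3). Assumed, because the documents give no value:
- correlation r between SUVmax and log volume
- volume hazard ratio of 1.5 or 2.0 per SD
- about 60% of participants with an event within 5 years (about 24 of 40)
- no effect of uptake itself

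**Approximation.** With no true uptake effect, the uptake-only hazard ratio per SD is roughly exp(r × ln HR for volume):
- r = 0: exp(0) = 1.00
- r = 0.3: exp(0.3 × 0.405) = 1.13 and exp(0.3 × 0.693) = 1.23
- r = 0.5: exp(0.5 × 0.405) = 1.22 and exp(0.5 × 0.693) = 1.41

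**Simulation.** 1,500 trials per setting, n = 40, exponential event times censored at 5 years, two-sided Wald test at a nominal 5%.

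| r | Volume HR per SD | Uptake-only HR | Rejection, uptake only | Uptake HR with volume in model | Rejection with volume |
|---|---|---|---|---|---|
| 0 | 1.5 | 1.01 | 4.9% | 1.01 | 5.3% |
| 0 | 2.0 | 1.01 | 5.1% | 1.00 | 5.3% |
| 0.3 | 1.5 | 1.12 | 8.8% | 0.98 | 6.9% |
| 0.3 | 2.0 | 1.20 | 14.1% | 1.00 | 4.9% |
| 0.5 | 1.5 | 1.22 | 15.1% | 1.02 | 5.9% |
| 0.5 | 2.0 | 1.37 | 29.9% | 1.01 | 5.6% |

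**Sensitivity.**
- A second set of simulations added random dropout and used n = 28 (about 20 events) and n = 40 (about 28 events). Uptake-only rejection was 7.3% to 15.6% at r = 0.3 and 11.8% to 31.7% at r = 0.5. With volume in the model it was 3.6% to 6.3%. Here 28 = 0.70 × 40 is only an illustrative reduction, since the 70% in 10.4 is a lesion-level figure.
- At weak correlation (0.1 to 0.2, volume HR 1.2 to 2.0) the false hazard ratio was 1.02 to 1.13 and rejection 4.5% to 8.8%.
- OS and PFS were not simulated separately. Fewer deaths than progressions would lower the rejection rate for OS, but would leave the bias in the hazard ratio much the same.

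**Cost of adjustment.** The standard error of the uptake coefficient grows by about 1/√(1 − r²): 1/√0.91 = 1.05 at r = 0.3 and 1/√0.75 = 1.15 at r = 0.5.

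**The case against.** The strongest reply is that this is a missing phrase in one exploratory bullet. The objective in 1.1.3 asks about uptake and survival, and an unadjusted association answers it. Nothing in 1.1.3, 10.3 or 10.7 claims that uptake is prognostic independently of tumor burden. Adjusting for volume would not isolate uptake either, since 3.1 allows several local treatments and section 4 permits systemic therapy. Most of this stands, and it sets the severity.

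Three stronger readings are tempting, and the documents do not support them:

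- *That 10.3 makes volume an adjuster for SUVmax.* It lists volume as a second quantity to be related to survival. Nor does 10.7 say that the model is univariable; it simply names no other term.
- *That the protocol shows uptake to depend on lesion size.* The remark in 1.2.1 that "there were a few small lesions only visible at 2 hours" concerns prostate cancer lesions and visibility, and the same passage says that most lesions were seen by 1 hour. The 1 cm limit in 10.8 is a condition in a futility rule. Both are indirect at best, and neither gives an SUVmax-volume correlation in HCC. Section 1.3.3 also cites a tissue study in which vascular PSMA expression could serve as an independent prognostic marker.
- *That an uptake effect would simply be a size effect.* At zero correlation there is no distortion, and at weak correlation it is small.

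One further objection stands. The documents do not say how the volume of interest is delineated. If it is segmented on uptake, volume itself carries uptake signal, and a joint model could remove part of a real association. That is a reason to report both estimates, not to leave volume out.

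**Conclusion.** The mismatch between 10.3 and 10.7 is real, and no other section closes it: volume is a stated survival endpoint without an analysis. That an uptake-only hazard ratio could partly reflect tumor size is a possibility, not a demonstrated bias. Its size rests wholly on assumed inputs. With a volume hazard ratio of 1.5 to 2.0 per SD and no true uptake effect, the false hazard ratio runs from about 1.0 at correlation 0 to 1.1–1.2 at 0.3 and 1.2–1.4 at 0.5. Across both sets of simulations, the nominal 5% rejection rate rises to about 7%–16% at 0.3 and 12%–32% at 0.5. Section 10.7 sets no significance level for this analysis, so these rates describe how easily a misleading result could arise, not a formal error rate of the plan.

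Severity is minor. The analysis is exploratory, and the primary endpoint, the sample size and the secondary analyses are untouched.

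**What to change.** Replace the Cox bullet in 10.7 with:

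> Cox regression of PFS and of OS on baseline SUVmax (highest target-lesion value per participant) and on log summed target-lesion volume, each alone and then entered together; unadjusted and mutually adjusted hazard ratios are reported with 95% confidence intervals as exploratory.

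Summed target-lesion volume is specified because 6.3.1.1 establishes volume extraction for target lesions only; a total tumor volume might need further segmentation.

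Also state:
- how the volume of interest is drawn, in particular whether its boundary depends on uptake
- how SUVmax and volume are assigned to participants with a negative baseline scan and a confirming biopsy, who stay in follow-up under 3.1 and 3.3

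The cost is wording plus those two definitions, with no new visit, scan or sample. The statistical price is one more covariate with few events, an uptake standard error about 5% larger at correlation 0.3 and 15% larger at 0.5, and possible over-adjustment if the volume is defined by uptake. Keeping the unadjusted estimate alongside guards against the last.

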10.8 INTERIM FUTILITY ANALYSIS AND EARLY STOPPING RULE

To avoid excessive expense and radiation exposure, if ¹⁸F-DCFPyL PET/CT is not successful in identifying lesions, we will implement the following interim futility analysis and early stopping rule.

We plan to stop the protocol if the first 5 participants with lesions greater than 1 cm have negative DCFPyL uptake (defined as tumor uptake less than adjacent background soft tissue, or less than blood pool for lymph nodes).

11 COLLABORATIVE AGREEMENTS

11.1 TRANSFERS ASSOCIATED WITH CORRELATIVE STUDIES CONDUCTED UNDER AN APPROVED PROTOCOL

Investigators in the NIH intramural program may participate in multi-site clinical trials (either as a site or as the coordinating center) under which human materials are transferred from the intramural program to another site for correlative studies that are part of the approved protocol. In such a situation, the protocol clearly documents the tests conducted under the correlative studies, and each institution participating in the clinical study is bound by the terms of their Protocol and their obligations under the statutes and regulations. In addition, intramural protocols are cleared by the IC Clinical Director. In such situations, use of an HM-MTA is not necessary for these transfers.

